For pregnant women enrolled in the study, each woman will be assigned a unique study ID. The information linking the women's personal information and study ID will be kept in a separate locked, password protected file only accessible by study personnel. For other study participants, we will not collect personal identifiers on any of the questionnaires, in-depth interviews, or focus group discussions and transcripts.

A study logbook will also be maintained to track providers participating in the study including the provider name, study ID, date of interview and interviewer. This logbook will be kept by the data coordinator at each facility in a locked, secure place during data collection along with logbooks referenced above. This will only be accessible by the counselor and Jhpiego/MCSP study staff. The names of providers will not be entered into the electronic database and the logbook will be destroyed 6 months after completion of the study.

VI. Data Custody, Security, and Confidentiality Protections

The sections below describe types of data sources and how they will be protected. For the type(s) of data you will have, put an "X" in the appropriate box to the left of the section that best describes how you will minimize the risk of a breach of confidentiality for your study. Note, as appropriate, how you will record/store data. These descriptions represent MINIMAL measures; you may add more stringent protections and other relevant information in B.

Confidentiality: The LOSS OR THEFT of 1) original/duplicate version of physical data collection instruments (forms, tapes, etc) or 2) physical devices containing electronic data (i.e. laptop/mobile device, external flash drive(s), is a threat to subject confidentiality. Risk of such a loss/theft is increased during movement/transport of data (in any format), such as in a vehicle or other move. Be sure to train anyone (co-investigators, staff, students, etc.) who might be engaged in the oversight of data handling/storage about this problem. Some typical risk-mitigation strategies would include:

- minimizing the physical movement of data and/or devices containing data
- encrypting electronic data (especially when stored on any mobile device, including flash memory tools, phones, tablets, etc, or when transferring across networks)
- making use of reliable courier services (FedEx, DHL, etc) when physical transport of bulk data forms is necessary
- minimizing the transfer of identifiable data in physical or electronic form (i.e. removing/separating/destroying identifiable data, when physical transfer of data is necessary)

A. Data Storage

1. Hard Copies of Data Collection Forms.	
	This activity will not involve receiving and/or accessing hard copies of data
X	Health workers and volunteer. Data collection forms RECORD NO PERSONAL IDENTIFIERS connecting study participants, and there are no codes providing a link. Data are anonymous.
	Data collection forms INCLUDE IDENTIFIERS. The forms are locked in a secure cabinet or room with limited access by authorized individuals. Forms will be kept in study team's possession during transport and will not be left unattended in a vehicle. When possible, de-identified copies will be used for coding and analysis.
X	Women's survey. Data collection forms ARE CODED with study participants' random study ID numbers. Codes/links between study IDs and identifiers are stored securely in a separate place (locked storage cabinet or secure electronic database.)
	Other:

2. Electronic Data	
X	Audio files of health workers and volunteers. The data do not contain personally identifiable information
X	Women's survey. These data are stored on a secure server protected by limited access and strong password systems. Data are coded when possible. Portable electronic devices will not contain identifiable information unless encrypted.
	Other:
3. Other Identifiable Data Storage, Retention, and Destruction (Audiotapes, videotapes, photographs, etc.) will be retained and stored securely (locked in cabinet or room) until:	
X	Transcription is complete, then audio files will be destroyed a maximum of 3 months later.
	Analysis is complete, then will be destroyed.
X	Study is complete and file is closed.
	Indefinitely. Provide justification for indefinite retention:
4. Existing Biospecimens to be used in this study: N/A	
	HAVE NO PERSONAL IDENTIFIERS.
	INCLUDE IDENTIFIERS AND ARE CODED; the PI will not have access to the link or code connecting the identifiers to the specimens.
	INCLUDE IDENTIFIERS, and the PI has access to those identifiers or to the link/code connecting specimens to individuals. The identifiers and/or code will be stored securely until the study is complete.

B. Certificate of Confidentiality

Will the study data stored in the United States be protected by a Certificate of Confidentiality? If yes, explain who will apply for and maintain the Certificate. (http://grants.nih.gov/grants/policy/coc/appl_extramural.htm)
N/A

C. Data Security and Sharing

PIs have the responsibility for responsible stewardship of data and protecting data confidentiality. This responsibility includes protecting physical custody of the data, storage and sharing with appropriate data use agreements that contain the appropriate security provisions. Describe any additional plans beyond those identified in the table that you have for storing and sharing the study data and/or materials, and how responsibility for the data will be managed. Include the following details:

1. Where will the study data be stored?
2. Who controls access to the data?
3. Will data be shared only if de-identified?
4. What additional (if any) security controls will be in place?

Data will be collected either on paper or on mobile devices. The women's surveys will be captured on mobile devices, while the health worker and volunteer data will be captured on paper and with audio-recordings. In general, the data collectors will keep the completed questionnaires securely in sealed envelopes and bring them back to the Jhpiego/MCSP Ethiopia office once the data collection is finished. Study personnel (e.g., supervisors and the study manager) will be allowed access to the written data during the field work. Once the Jhpiego/MCSP Ethiopia Study Manager obtains the completed data collection forms, the data will be entered into electronic databases on password-protected computers at the MCSP office. Hard copies will be stored in locked cabinets in the Jhpiego/MCSP Ethiopia office. Names and participant identifiers will be maintained in a study log book that is kept locked in a separate location from the completed data collection forms. At all times, the data will be treated confidentially and only the study staff

will be allowed access to the raw data. De-identified and/or aggregate data may be analyzed by the study team. Data collected on tablets using a software that allows for data encryption.

VII. Risks of the Study

- A. Describe the risks, discomforts, and inconveniences associated with the study and its procedures, including physical, psychological, emotional, social, legal, or economic risks, and the risk of a breach of confidentiality. These risks should be described in the consent documents.

There are no anticipated physical risks for participation in this study. The potential non-physical risk for recent mothers and health workers include their personal information being shared with the study personnel, Ministry of Health personnel or community members. This can be considered minimal risk, as little or no information of a confidential nature will be collected. All information collected during the assessment will be treated as confidential. During focus group discussions, some participants might feel a bit uncomfortable discussing some of the topics. This will be mitigated by assuring the participants of confidentiality of information during the consent process. Participants will also be assured that they may choose not to continue with the questionnaire or focus group at any time. Furthermore, study identifiers will be used on paper and in electronic database further ensuring confidentiality.

- B. Describe the anticipated frequency and severity of the harms associated with the risks identified above; for example, if you are performing “x” test/assessment, or dispensing “y” drug, how often do you expect an “anticipated” adverse reaction to occur in a study participant, and how severe do you expect that reaction to be?

Expected harm as a result of participating in this study is minimal for all participant types.

- C. Describe steps to be taken to minimize risks. Include a description of your efforts to arrange for care or referral for participants who may need it.

Interviews will be administered in a private area within the homestead or nearby – respondents will not be required to travel away from their homes in order to participate. These respondents and health providers will assist in identifying a suitable location.

- D. Describe the research burden for participants, including time, inconvenience, out-of pocket costs, etc.

The only burden for respondents is time they spend participating in an interview. There will be no payments or monetary compensation of study participants since the interviews will be done at their homes.

- E. Describe how participant privacy will be protected during data collection if sensitive questions are included in interviews.

Private locations will be located for interviews to project participant privacy. No sensitive questions, such as HIV status, will be asked.

VIII. Direct Personal and Social Benefits

- A. Describe any potential direct benefits the study offers to participants (“payment” for participation is not a direct personal benefit).

There will be no direct benefits to individual study participants; they will not receive any payment or other compensation.

- B. Describe potential societal benefits likely to derive from the research, including value of knowledge learned.

It is expected that through the study information; community level coverage of PFP knowledge and services will improve which may lead to improved health situation or outcomes in the community.

IX. Payment:

- A. Describe the form, amount, and schedule of payment to participants. Reimbursement for travel or other expenses is not “payment,” and if the study will reimburse, explain.

No payment will be made to study participants.

X. Study Management

- A. Oversight Plan:

1. Describe how the study will be managed.

The PI will oversee the study. She will work with the study team to carefully establish study procedures, including human subject protection, training tools for data abstractors and data collection steps. She will be in regular contact with the study team and provide oversight for data collection, review, analysis and report writing. In Ethiopia, there will be a co-investigator and study manager to recruit data abstractors, oversee and manage the data collection at health facilities. This person will be responsible for local data management, texts and phone calls with providers. The co-investigators are expected to lead the orientation of study managers and support training of data abstractors. The study managers will be drawn from M&E staff in the Jhpiego office in Ethiopia. The PI will establish weekly check in calls during the data collection period with the co-PIs responsible for data collection to review procedures, challenges and discuss opportunities to explore additional datasets.

2. What are the qualifications of study personnel managing the project?

[name], MHS, is the PI and is the Family Planning Team Leader for the global USAID-funded Maternal and Child Survival Program. She is responsible for interactions with the donor funding this study in addition to managing oversight of the study.

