This study will be implemented 2 primary health care units (PHCUs), comprised of one health center and all kebeles/health posts in their catchment area, in Hitosa Woreda and 2 PHCUs in Lude-Hitosa Woreda. We randomly assigned 1 PHCU in each Woreda to the intervention and control arms. So out of 4 PHCUs in each Woreda, 1 was selected for intervention and 1 for control.

We obtained the total population for each PHCU. To estimate the number of women age 15-49 and expected pregnancies at the time of study survey, we used results from the Ethiopia mini DHS 2014: 43.6% of female residents of selected households were age 15-49 and 7.3% of women age 15-49 were currently pregnant at the time of the Mini DHS 2014.

Table 3: Estimation of eligible population

Arm	Total population	Female population (50%)	Expected females age 15-49 (43.6% of female pop)	Expected current pregnancies (7.3% of women 15-49)	Women 6-9 months pregnant (pregnancies / 3)
Intervention	72,138	36,069	15,726	1148	382
Comparison	52,508	26,254	11,446	835	278

For pregnant women, we calculated the minimum sample size requirements for this quasi-experimental design for the main outcome of interests (adoption of LAM and other modern method by 12-month PP) using the formula:

$$n' = \frac{\{z_{1-\alpha/2}\sqrt{2\bar{p}(1-\bar{p})} + z_{1-\beta}\sqrt{p_1(1-p_1) + p_2(1-p_2)}\}^2 (1 + (m-1)\rho)}{(p_1 - p_2)^2}$$

where, $p = (p_1 + p_2) / 2$

Where p_1 and p_2 are the proportions of women adopting LAM or other modern method in the intervention and control arms, respectively, and Z's are the critical value of the normal distribution at $\alpha=0.05$ and $\beta=0.20$; $1+(m-1)\rho$ captures the design-effect due to cluster based sampling of areas, where m = average size of the clusters and ρ =intra-cluster correlation. We consider a design-effect (deff) of 1.5 for adjusting higher intra-cluster correlation in the observations in the quasi-experimental design.

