We require a minimum of 299 women in postpartum observation period in each arm to detect an increase of at least 10% contraceptive prevalence rate (CPR) in the intervention arm, compared to the women in the control arm (20% vs 10% in the intervention and control arm, respectively) with $deff=1.5$ at 80% statistical power. Assuming about 20% lost-to-follow-up and non-response rate, we target to enroll 375 women in each arm. We consider that it will be sufficient to select 1 PHCU and its attached *kebeles* in each of the two *woredas* to ensure adequate sample size, with 2 PHCU randomly assigned to the intervention area (1 per *woreda*) and 2 to the control area (1 per *woreda*). The eligible women in 3rd trimester who consent to participate in the study voluntarily will be recruited and be interviewed at enrollment and at 12-month PP.

We used $p_1=0.2$ (20% PP contraceptive uptake by the final round of observation in the intervention arm) and $p_2=0.1$ (10% in the comparison arm). We considered $deff=(1+[m-1]\rho)= 1.5$. Because we are targeting 375 sample size of pregnant women in each arm consisting of 2 PHCUs, this implies $m=188$ AND $\rho=0.0027$.

Because the selected PHCUs are adjoining *woredas* of the same zone, it is expected that they will be quite similar, and in addition, the underlying population are all similar in terms of postpartum status; hence ρ very small (the larger the heterogeneity, the larger the ρ value). The Ethiopia DHS 2011 results suggest that the $deff$ of contraceptive use in all 11 regions are much smaller than the national level $deff$ of CPR (Appendix B – Estimates of Sampling Errors); *woreda* level $deff$ is expected to be much smaller due to less heterogeneity at *woreda* level, compared to the region/state level. In all regions, method specific $deff$ was <1.5 . So, we considered that of $deff=1.5$ is applied in this study is reasonable and practical. A study on postpartum use of contraceptive method at a *woreda* level in Ethiopia also had $deff=1.5$ (Abera Y, Mengesha ZB, Tessema GA. Postpartum contraceptive use in Gondar town, Northwest Ethiopia: a community based cross-sectional study. BMC Women's Health. 2015;15:19.)

Sample size requirements are included below based on the average number of providers and HDAs and managers in each *kebele*. See Table 4: Sample Size Summary

Table 4: Sample Size Summary

Study Participant	Intervention (2 PHCU)	Comparison (2 PHCU)	Total
Pregnant women	375	375	750

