Facility Providers working in ANC, L&D, postnatal care, immunization, family planning	10	10	40
District managers and stakeholders	Not applicable	Not applicable	6
Health Extension Workers (10 HPs in intervention clusters and 8 in comparison clusters; each HP has 2 HEWs)	20	16	36
HDA/HDA Team Leaders (2 FGD/PHCU, 10 people per FGD)	40	40	80
Total Sample Size	455	449	910

Since the expected number of eligible women in the selected control PHCUs is less than we require to meet this sample size, we will enroll women from adjoining kebeles (villages) in non-study PHCUs to reach the required sample size. The kebeles will be selected with local leadership and with the aim to minimize contamination by selecting villages further from the intervention PHCU. If we do not reach the required sample size in intervention PHCUs, we will also select adjoining kebeles to each the sample size minimum; the HEWs and HDA from these will be trained in the intervention package. All health centers in the entire woreda are receiving the same strengthening inputs, so no additional inputs will be necessary.

IV. Participants

Describe the study participants and the population from which they will be drawn. Specify the inclusion and exclusion criteria. If you plan to include children, note their ages and whether you will include children in foster care. Note if the participants are particularly vulnerable in terms of cognitive limitations, education, legal migration status, incarceration, poverty, or some combination of factors.

A. Inclusion criteria:

- Pregnant women (including emancipated minors)
- Providers (HDA, HEW, HCW, district managers providing PFP messages or services in study area)
- Willing to give informed consent

C. Exclusion criteria:

- Non – pregnant women, women living outside study area, facility providers not working in ANC, L&D, PNC or immunization. Providers from other points of service study facilities.

NOTE: If you are recruiting participants or receiving, accessing, or using data from a U.S. health care provider, HIPAA review is likely to be required. If you plan to bring identifiable health information from a foreign country to a U.S. covered entity (e.g., lab at the Hopkins SOM), HIPAA may be triggered. Check “yes” to the HIPAA question in the PHIRST application.

V. Study Procedures

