#### A. Quantitative interviews with Women:

After data have been thoroughly examined for quality, the study team will perform exploratory data analysis of key variables such as checking frequency distributions, measures of variability, central tendency, and data outliers. We will also check for incomplete data and consider strategies to handle missing values such as undertaking an imputation strategy and weighting adjustments for non-responses.

We will compare differences by study arm for key variables. Analysis will account for clustering of variables at kebele (village) level using the Taylor linearization method. Differences between the arms for categorical variables will be assessed using the Pearson chi-squared test with the Rao-Scott correction. Differences in continuous variables will be assessed using an adjusted t-test. In case of substantial differences between the study arms, we will perform propensity score matching and perform the analysis with inverse probability weights.

Key descriptive variables:

- Sociodemographic data such as age, marital status, education, and socioeconomic status (nationally representative SES will be determined using the EquityTool described here: <http://www.equitytool.org/>)
- (Baseline only) Proportion of pregnant women with non-first pregnancies (non-primiparous) who previously used family planning
- Number of health system contacts where FP was discussed or provided, by type of contact (ANC, PNC, immunization, etc) and provider (facility provider, HEW, volunteer)
- Proportion of postpartum women who chose a method prior to delivery, by method, and received chosen method
- Proportion of postpartum women who used FP during the first 12 months after giving birth, by method
- Reasons for starting and stopping contraceptive methods and duration of use

- Initiation and duration of exclusive breastfeeding and lactational amenorrhea (LAM); average/median duration of postpartum amenorrhea, PP sexual initiation/PP abstinence
- Partner communication about family planning

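### The stated 80% power takes no account of only four PHCUs being assigned, and the planned kebele-level test largely leaves out variation between PHCUs

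*Protocol*

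**What the plan says.** Protocol section III.B describes the allocation: "We randomly assigned 1 PHCU in each Woreda to the intervention and control arms". That makes four assigned PHCUs, two per arm. The sample size formula in the same section uses normal critical values at alpha 0.05 and beta 0.20, and requires 299 women per arm for "20% vs 10% in the intervention and control arm, respectively) with $deff=1.5$ at 80% statistical power". Allowing for 20% loss, the target is 375 enrolled per arm.

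The section treats the PHCU as the cluster: "Because we are targeting 375 sample size of pregnant women in each arm consisting of 2 PHCUs, this implies $m=188", with rho = 0.0027. It defends the size of the design effect by pointing to survey design effects and to the similarity of adjoining woredas. It does not discuss having two clusters per arm.

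SAP section A works at a different level: "Analysis will account for clustering of variables at kebele (village) level using the Taylor linearization method". The primary logistic model is likewise adjusted for kebele clustering only. The SAP names no PHCU term, no woreda stratum or pairing, no small-cluster correction and no reference distribution for the test.

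Protocol Table 3 expects 278 eligible women in the control PHCUs. To make up the number, the text after Table 4 says "we will enroll women from adjoining kebeles (villages) in non-study PHCUs to reach the required sample size".

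**The concern.** A design effect inflates the variance for clustering. It does not allow for how poorly that variance is known when it must be estimated from two clusters per arm. Normal critical values treat it as known, so the 80% is not what a comparison of the assigned units would deliver.

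The SAP sidesteps the shortage of units by moving to kebeles, of which there are more. But kebeles sit inside PHCUs, and the PHCU was assigned. Differences between PHCUs that have nothing to do with the intervention then enter the arm contrast, while only a small part of them enters its standard error.

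Two readings of the result are at stake. A null finding would be taken as coming from an 80%-powered comparison. A positive finding would be taken as a 5% test, although it may be less strict than that.

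**Working it through.** **Inputs.** From Protocol III.B: p1 = 0.20, p2 = 0.10, two-sided alpha 0.05, deff 1.5, 299 analysed per arm, m = 188, rho = 0.0027, two PHCUs per arm. From Table 4: "10 HPs in intervention clusters and 8 in comparison clusters; each HP has 2 HEWs". The 18 health posts stand in for kebeles, which is an assumption.

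**1. The plan's own figures.** With mean proportion 0.15, the formula gives (1.960 × √0.255 + 0.842 × √0.25)² / 0.10² = 198.96. Then 198.96 × 1.5 = 298.4, so 299. Next, 299 / 0.8 = 373.75, against a target of 375. Finally rho = 0.5 / 187 = 0.0027. With normal critical values, 299 per arm at deff 1.5 gives 80.1% power. All of this reproduces.

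**2. Power at the level of assignment.** SE = √((0.16 + 0.09) × 1.5 / 299) = 0.0354, so the noncentrality is 0.10 / 0.0354 = 2.82. At deff 1.0 (rho = 0), SE = √(0.25 / 299) = 0.0289 and the noncentrality is 3.46. Four PHCU means leave 2 + 2 − 2 = 2 df. Two within-woreda differences leave 1 df. Noncentral-t power:

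| Comparison | Critical value | deff 1.5 | deff 1.0 |
|---|---|---|---|
| Unpaired, 2 df | 4.303 | 35.6% | 47.0% |
| Paired by woreda, 1 df | 12.706 | 17.5% | 21.4% |

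The loss comes mainly from the critical value, so arguing that rho is tiny does not restore 80%.

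**3. False positives of the kebele-level test.** This was simulated with 40,000 trials per setting, 299 women per arm, 10 and 8 kebeles nested in 2 + 2 PHCUs, a variance linearised at kebele level and no covariates. Rates below are for 10% uptake in both arms; the ranges for added kebele correlation also cover 20% in both arms. At about 150 analysed women per PHCU, rho = 0.0027 is a deff of 1 + 148.5 × 0.0027 = 1.40.

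| Where the variance lies | t, 16 df | Normal |
|---|---|---|
| No PHCU variance | 5.1% | 6.8% |
| rho = 0.0027, all between PHCUs within a woreda | 8.5% | 11.1% |
| Same, plus an assumed kebele correlation of 0.01 to 0.02 | 7.0% to 7.6% | 9.1% to 9.9% |
| rho = 0.0027, all between woredas | 4.7% | 6.3% |

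A further simulation on the same layout, with rho split half within and half between woredas, gives about 6.7% with t. In the second row the true design effect is about 1.40 and the kebele-level variance recovers about 1.05. It therefore captures 0.05 of the 0.40 inflation, or one eighth. With a normal reference, part of the excess comes from having few kebeles: the rate is already above 6% with no PHCU variance.

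**4. Top-up.** 375 − 278 = 97 control women, and 97 / 375 = 26%. A simulation with three or four extra control kebeles in one to three extra PHCUs (assumed numbers) gives 6.7% to 7.6% with t at rho = 0.0027.

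**The case against.** The protocol does not claim 80% power without conditions. It ties the figure to deff = 1.5 and argues for that value: "So, we considered that of $deff=1.5$ is applied in this study is reasonable and practical". It also presents 1.5 as cautious, since it expects woreda-level design effects to be smaller than regional ones. This stands as far as it goes. The missing condition is the number of assigned units, which no value of deff supplies.

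Three stronger readings are tempting, and the documents do not support them.

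- **That the planned analysis has 36% power.** The 36% and 18% belong to tests the SAP does not plan. Power for the kebele-level test needs a kebele correlation, which neither document gives.
- **That the planned test certainly exceeds 5%.** This needs between-PHCU variance within woredas. Each woreda supplies one PHCU to each arm, so variance between woredas cancels from the contrast. The documents do not say how rho divides. Moreover, 0.0027 was solved back from an assumed deff, so it is a planning value and not an estimate. A survey design effect depends on that survey's cluster size and cannot confirm it at m = 188.
- **That kebele-level standard errors contain no PHCU variance.** Kebele residuals around the arm mean pick up a small part of it.

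The top-up might be said to add control clusters. It may, and it slightly lowers the simulated error rate, but those PHCUs were not randomly assigned. Four remains the number of assigned units. Nor does the quasi-experimental label answer the point, because the protocol still states a power and the SAP still tests arm differences.

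**Conclusion.** The concern holds in a conditional form. The sample size arithmetic is correct, but the 80% treats the clustering variance as known. A comparison at the level of assignment has about 36% power on 2 df at deff 1.5, at most 47% even at rho = 0, and about 18% on 1 df with the pairing kept. These figures assume two PHCUs per arm and 299 analysed women per arm.

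The kebele-level test largely omits between-PHCU variance. Its false-positive rate is about 7% to 9% with t on 16 df, or 9% to 11% with a normal reference, if rho = 0.0027 lies between PHCUs within a woreda. With t it falls towards 5% as the variance moves to between woredas. That range rests on 18 health posts as a proxy for kebeles and an unadjusted comparison. The planned covariate adjustment and possible propensity weighting were not simulated. The documents should be corrected because the restatement costs almost nothing and changes how either result is read.

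**What to change.** No change to enrolment, estimand or planned analysis.

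1. In Protocol III.B, replace the power statement with:

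> 80% power under normal critical values with deff = 1.5 treated as known. Because only two PHCUs per arm were assigned, a comparison at the level of assignment has about 36% power (2 df), at most 47% even at rho = 0, and about 18% (1 df) if woreda pairing is kept.

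2. In Protocol III.B and SAP section A, add:

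> Kebele-level standard errors largely omit variation between PHCUs, the unit of assignment. A non-significant result should not be read as coming from an 80%-powered comparison. The test may reject a true null more than 5% of the time if PHCUs differ within woredas (about 7% to 9% with t, or 9% to 11% with z, at an assumed within-woreda rho of 0.0027).

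3. Note beside these that the figures assume two PHCUs per arm, and that about 97 of the 375 control women are expected to come from PHCUs that were not randomly assigned.

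The cost is a short paragraph in the protocol and a few sentences in the SAP. The downside is a much less favourable stated power.
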